7.4.1.1 Initial CLAAS and Next Generation CLAAS Systems

The Initial CLAAS System (including the access sheath, delivery catheter, and implant) was used from the beginning of the study enrollment in June 2022 through the end of April 2024. In April 2024, Conformal initiated several changes to the CLAAS System, referred to in this Clinical Investigational Plan as Next Generation CLAAS. These included reducing the height of the anchors on the implant, modifying the orientation of the ePTFE layers of the implant, improving the kink resistance and torque transmission of the Access Sheath and Delivery Catheter, reducing the stiffness of the dilator, and redesigning the delivery catheter handle to improve ergonomics, reliability, and performance.

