8.8.2 Conscious Sedation Population

The Conscious Sedation ITT subject is an individual who signs an ICF, has been assigned to the Conscious Sedation Cohort and has an implant procedure attempted. For this population, an implant procedure attempt (ITT established) is defined when the CLAAS Delivery Catheter is introduced into the body.

If an implant procedure is attempted without an implant placed, the subject must be followed through the Primary Safety and Efficacy Endpoints (at all visits including 7-days, 45-days, 6-months, 12-months, and 18-months) assessing only: QVSFS, AE Assessment, and Concomitant Medication Assessment. These assessments can be conducted via telehealth/phone call. These subjects will not be required to have subsequent protocol mandated imaging and will not be required to follow the medication requirements. If a subject in the Conscious Sedation Population experiences a suspected stroke or systemic embolism, that subject should be

brought in for an Unscheduled Visit (in-person clinic visit) for assessment per the Schedule of the Assessments matrix. After the 18-Month visit, these subjects will have completed all required study assessments.

Subjects who are scheduled for a conscious sedation procedure, but no longer meet eligibility criteria and do not have a procedure attempt (i.e., the CLAAS Delivery Catheter never entered the body) will be followed only through 45 days via telehealth/phone call visits. No protocol mandated imaging or medication therapy will be required. After the 45-Day visit, these subjects will have completed all required study assessments and will be classified as Screen Failures.

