8.8.4 Attempted Population

The Attempted Population includes all ITT subjects in whom a LAAO procedure has been attempted, i.e., the LAAO access sheath was inserted into the body.

The Attempted Population includes two groups: 1) subjects who undergo LAAO Procedure and receive a LAAO Closure Device and 2) subjects in whom a undergo the procedure without receiving a LAAO device.

Following index procedure hospitalization discharge, these subjects in the Attempted Population who do NOT receive an implant will not be required to have subsequent protocol mandated imaging and will not be required to follow the medication requirements. Subjects who do not receive an implant must be followed through the Primary Safety and Efficacy Endpoints with telehealth/phone call visits (at all visits including 7-days, 45-days, 6-months, 12-months, and 18-months) assessing only: QVSFS, AE Assessment, and Concomitant Medication Assessment. If a subject in the Attempted Population group experiences a suspected stroke or systemic embolism, that subject should be brought in for an Unscheduled Visit (in-person clinic visit) for assessment per the Schedule of Assessments matrix. After the 18-Month visit, these subjects will have completed all required study assessments.

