- cardiac perforation,
- pericardial effusion requiring drainage,
- ischemic stroke,
- device embolization,
- major vascular complications

Statistical Considerations:

The sub-study is designed to demonstrate non-inferiority in CLAAS Implant success compared to the CLAAS arm of the RCT, based on the 45-day endpoint assessment. It is estimated that a total sample size of 130 subjects (including 6% attrition) is required to demonstrate non-inferiority. This estimated sample size will be verified and adjusted, if necessary, based on the observed rate of CLAAS Implant success rate in the RCT, prior to initiation of the sub-study.

J. Sample Size Determination

Subjects are enrolled in the Conscious Sedation Sub-Study when the subject has signed informed consent and has the procedure scheduled.

The Conscious Sedation Sub-Study will be analyzed by comparing subjects from the sub-study with subjects who receive the CLAAS Implant from the randomized cohort. The primary endpoint for the Sub-Study is Procedure Success at 45-days, defined as:

 successful implantation of the LAAO Device in the LAA with acceptable position, and complete closure or peri-device residual leak ≤5 mm in width on TEE, as evaluated by independent core lab [at 45 days post-procedure] and without inhospital major procedure-related complications during hospitalization or at 7 days whichever is first.

The goal of the Sub-Study will be to demonstrate non-inferiority between the two procedural techniques based on the Procedure Success at 45-day endpoint.

The endpoint will be assessed with the following non-inferiority hypothesis:

 H_0 : Pt - Pc \leq -0.10 H_A : Pt - Pc > -0.10

where Pt and Pc are the proportion of subjects with Procedure Success at 45-days in the treatment and control groups respectively and 0.10 represents the non-inferiority margin. The hypothesis will be evaluated using a one-sided 95% confidence interval for the difference in proportions based on a Farrington-Manning non-inferiority test. If the one-sided upper confidence bound for the difference is less than the non-inferiority margin, the objective will be met, and the treatment group will be non-inferior to the control group for the primary effectiveness endpoint.

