It is anticipated that the Procedure Success for the CLAAS procedure with general anesthesia will be between 90-95%. As such, using a non-inferiority margin of 10%, and a one-sided 0.05 alpha level, a total of 130 subjects (including attrition of 6%, e.g., 122 evaluable subjects) in a conscious sedation sub study versus approximately 600 CLAAS subjects from the overall

randomized RCT would provide greater than 90% power. Calculations are based on a Farrington-Manning test of non-inferiority for binomial proportions.

The final statistical details will be confirmed as an amendment to the Statistical Analysis Plan prior to the enrollment of Sub-Study subjects.

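### Appendix E compares sub-study subjects with RCT subjects who received a CLAAS implant, on an endpoint that includes implantation, and sub-study and RCT attempts start at different steps

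*Protocol*

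**What the plan says.** **Comparator.** The one sentence that says how the sub-study will be analysed is in Appendix E, part J: "The Conscious Sedation Sub-Study will be analyzed by comparing subjects from the sub-study with subjects who receive the CLAAS Implant from the randomized cohort". The Statistical Considerations paragraph just above it states a different group: "The sub-study is designed to demonstrate non-inferiority in CLAAS Implant success compared to the CLAAS arm of the RCT, based on the 45-day endpoint assessment". Sections 8.2.3 and 8.3.3 and Appendix E part A also name the CLAAS arm. The power statement in part J sets 122 evaluable subjects "in a conscious sedation sub study versus approximately 600 CLAAS subjects from the overall" RCT.

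**Endpoint.** Procedure Success at 45 days begins with "successful implantation of the LAAO Device in the LAA with acceptable position". It adds a leak criterion on TEE and freedom from in-hospital major procedure-related complications.

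**Start of an attempt.** Section 8.8.2, for the sedation cohort: "For this population, an implant procedure attempt (ITT established) is defined when the CLAAS Delivery Catheter is introduced into the body". Section 8.8.4, for the RCT: "i.e., the LAAO access sheath was inserted into the body". Section 8.8.1 uses the access sheath for Roll-In as well. Part J gives a third entry point for the sub-study: "Subjects are enrolled in the Conscious Sedation Sub-Study when the subject has signed informed consent and has the procedure scheduled".

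**Device generation.** Section 7.4.1.1 says that the Initial system "was used from the beginning of the study enrollment in June 2022 through the end of April 2024". The sub-study starts only after RCT enrolment is complete (8.2.3).

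**The concern.** Two separate mismatches affect the same hypothesis test.

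First, restricting controls to implanted subjects conditions them on part of the outcome. A failed implant in the RCT leaves the comparator. A failed implant under sedation stays in the sub-study set and counts as a failure, whether that set is defined by 8.8.2 or by the entry rule in part J. Two equal techniques would then show a difference unfavourable to sedation, and the sample size makes no allowance for it.

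Second, the access sheath goes in before the Delivery Catheter. A sedation case abandoned at the sheath stage is not an attempt under 8.8.2, but the same case in the RCT is an attempt under 8.8.4. If the comparator is all RCT attempts, this removes early failures from the sedation side only, which favours sedation.

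The mismatches point in opposite directions and have unrelated sizes, so they cannot be assumed to cancel. Nor do they fully operate together: against an implanted-only comparator, sheath-stage failures are missing from both sides. The size and even the direction of the bias therefore depend on which sentences are followed.

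**Working it through.** **Inputs from Appendix E, part J:** 122 evaluable sub-study subjects (130 less 6%), about 600 comparators, margin 0.10, one-sided alpha 0.05, Farrington-Manning test, success 90% to 95%, stated power above 90%.

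**Inputs for the implant rate (context only):** section 6.4 reports 41 of 42 implants in feasibility phase 2, or 97.6%. Section 6.3 reports 15 and then 4 successful Prague cases. Together: (41 + 19)/(42 + 19) = 60/61 = 98.4%. The RCT implant rate is not known, so this range is an assumption.

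**Step 1: reproduce the stated power.** Power = Φ[(pt − pc + 0.10 − 1.645·s0)/s1], where s0 is the standard error under the null-restricted estimates and s1 the standard error at the true rates. With pt = pc = 0.90, s0 = 0.0374 and s1 = 0.0298:

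(0.10 − 1.645 × 0.0374)/0.0298 = 1.29, so power is 90.2%. Exact binomial enumeration of the same test gives 90.1%. At 0.95 the two figures are 98.3% and 97.7%.

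The stated figure reproduces when both groups are counted on the same basis.

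**Step 2: implanted-only comparator, equal techniques.** Let p be success among all attempts and r the implant rate, the same under both techniques. The sub-study shows p. The comparator shows p/r, because its non-implanted failures have been removed. The built-in difference is p − p/r.

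For p = 0.90 and r = 41/42, p/r = 0.922 and the difference is −2.2 points. With s0 = 0.0357 and s1 = 0.0293:

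(−0.0220 + 0.10 − 1.645 × 0.0357)/0.0293 = 0.66, so power is 74.6% (exact 75.5%).

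| p | r | p/r | difference (points) | power, normal | power, exact |
|---|---|---|---|---|---|
| 0.90 | 41/42 | 0.922 | −2.2 | 74.6% | 75.5% |
| 0.90 | 60/61 | 0.915 | −1.5 | 80.5% | 81.1% |
| 0.95 | 41/42 | 0.973 | −2.3 | 90.1% | 89.4% |
| 0.95 | 60/61 | 0.966 | −1.6 | 94.0% | 93.1% |

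**Step 3: later attempt definition, against all RCT attempts.** Put sedation at the null boundary: true success 82% against 92% (92% is assumed, within the 90% to 95% range). If a fraction f of sedation cases fails before the Delivery Catheter and is left out, the observed rate is 0.82/(1 − f).

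| f (assumed) | observed sedation rate | type I error, normal | type I error, exact |
|---|---|---|---|
| 0 | 82.0% | 5.0% | 4.6% |
| 1% | 82.8% | 7.5% | 7.2% |
| 2% | 83.7% | 11.1% | 10.9% |
| 3% | 84.5% | 16.0% | 16.2% |

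**The case against.** **The implanted-only comparator is not a settled rule.** Four other statements name the CLAAS arm, and the sample size is to be re-verified on the observed implant success rate in the RCT, which needs non-implanted subjects in its denominator. The part J sentence may only have been meant to separate CLAAS from Control subjects. This stands as far as it goes: the fault is a contradiction. But the sentence that describes the analysis picks the conditioned group.

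**A reader might infer that most of the power is lost.** An implant rate of 95% would give about 48% power at 90% success, and the pooled US feasibility rate of 59/64 = 92.2% about 17%. The documents do not support those rates for the RCT. Section 6.4 attributes the four phase 1 failures to appendages too large for the Regular device, treated before the Large one was available. The RCT has both sizes and excludes anatomy that does not fit.

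**A reader might infer that early sedation complications are hidden.** Section 12 collects adverse events from consent in the sub-study, and 8.8.2 and Appendix E part H follow subjects without an attempt to 45 days. The events are recorded. What is open is whether those subjects enter the efficacy denominator.

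**A reader might infer that device generation confounds the comparison.** The protocol never names the generation used in the sub-study, and the Initial-system share of the CLAAS arm is unknown. That supports a sensitivity analysis, not a change of primary comparator.

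**A positive result would survive the first bias.** True: it is conservative, so it costs power and does not inflate type I error. The second mismatch has no such protection.

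**Final details are deferred to an SAP amendment.** That leaves time to correct the text, but the protocol already fixes both definitions, and inconsistently.

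**Conclusion.** The point holds as two inconsistencies to be reconciled. The comparator in part J is conditioned on a component of the endpoint and contradicts the CLAAS-arm comparator named elsewhere. If followed, it takes power for equal techniques to about 76% to 81% at 90% success and 89% to 93% at 95%, assuming an implant rate of 97.6% to 98.4%. The shortfall is therefore clear at the lower success rate and small or absent at the higher one.

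The differing start of an attempt is a separate fault. It matters when the comparator is all RCT attempts, and would raise type I error to between 7% and 16% if 1% to 3% of sedation cases failed at the sheath stage. Those percentages are assumptions; the protocol gives no such rate.

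The stated power is not miscalculated. It belongs to a like-for-like comparison that the analysis sentence does not describe.

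**What to change.** - In Appendix E, define the comparator as all RCT subjects assigned to CLAAS in whom a procedure was attempted, and remove the implanted-only wording from part J.
- Use access sheath insertion as the single attempt definition for this analysis set, in 8.8.2 and Appendix E, matching 8.8.1 and 8.8.4. State that consent and scheduling mark enrolment, not entry to the analysis set.
- Say that an attempt without an implant counts as a failure in both cohorts.
- Add a sensitivity analysis with comparators restricted to the Next Generation system. It should not be primary: with 400 such comparators like-for-like power is 88.7% at 90% success and 97.5% at 95%; with 200 it is 84.8% and 96.3%. The number available is unknown.

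The cost is wording, carried into the SAP amendment already due before sub-study enrolment. No extra subjects are needed: the like-for-like set restores the stated power at about 600 comparators. If the definition in 8.8.2 itself changes, the follow-up that section requires for sheath-only cases must be restated with it.

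### The conscious-sedation sub-study's success rule uses the upper confidence bound for a success-rate endpoint, so as written it accepts sedation that is far worse

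*Protocol*

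**What the plan says.** Protocol Appendix E, J. Sample Size Determination, sets up the sub-study test in this order.

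- **Endpoint.** Pt and Pc are each a "proportion of subjects with Procedure Success at 45-days in the treatment and control groups respectively and 0.10 represents the non-inferiority margin". A larger value is a better result.
- **Hypotheses.** H0: Pt - Pc ≤ -0.10 against HA: Pt - Pc > -0.10.
- **Method.** "The hypothesis will be evaluated using a one-sided 95% confidence interval for the difference in proportions based on a Farrington-Manning non-inferiority test".
- **Decision rule.** The objective is met under the condition that ends this passage: "based on a Farrington-Manning non-inferiority test. If the one-sided upper confidence bound for the difference is less than the non-inferiority margin".
- **Sample size.** "using a non-inferiority margin of 10%, and a one-sided 0.05 alpha level", 130 subjects (122 evaluable after 6% attrition) against about 600 CLAAS subjects from the RCT give more than 90% power. General-anesthesia success is expected to lie between 90% and 95%.

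The section closes by saying that final statistical details will be confirmed in a SAP amendment before sub-study enrollment.

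**The concern.** The hypotheses and the decision rule in the same paragraph point in opposite directions. Non-inferiority on a success rate means ruling out that sedation is worse by 10 points or more. That is a statement about the lower bound of Pt - Pc. The upper bound only says how much better sedation could be.

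Sections 14.5.1 and 14.5.2 use the same wording for the RCT primary endpoints. It is right there, because those endpoints are adverse-event proportions with positive margins (0.032 and 0.058). Appendix E changes the endpoint to a success rate and reverses the hypotheses, but keeps the event-rate sentence.

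The sub-study is the means of addressing Objective 3, safe delivery of the device under conscious sedation. This sentence is the only place where the protocol says which observed result meets the sub-study objective; the sub-study's safety composite has no success criterion. Applied as written, the rule would allow a claim of non-inferiority for a technique that plainly fails.

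**Working it through.** **Inputs, all from Appendix E, section J.** nt = 122 evaluable, nc = 600, margin 10 points, one-sided alpha 0.05 (z = 1.645), comparator success 90-95%. Equal true rates in the two groups for the power calculation are an assumption of this check; the protocol gives a range for general anesthesia only.

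**Test statistic (Farrington-Manning).** For a reference difference d0,

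z(d0) = (p̂t - p̂c - d0) / √[p̃t(1 - p̃t)/nt + p̃c(1 - p̃c)/nc],

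where p̃t and p̃c are the maximum-likelihood estimates restricted to p̃t - p̃c = d0. In these terms:

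- Rule A, matching the hypotheses: lower bound > -0.10, that is z(-0.10) > 1.645.
- Rule B, the written rule with the stated margin: upper bound < +0.10, that is z(+0.10) < -1.645.
- Rule C, the written rule with the margin taken from H0: upper bound < -0.10, that is z(-0.10) < -1.645.

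**Step 1: reproduce the plan's power.** Under Rule A, power = Φ[(0.10 - 1.645·s0)/s1], with s0 the restricted and s1 the unrestricted standard error. At 90% success in both groups:

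- restricted estimates 0.8098 and 0.9098, so s0 = √(0.8098·0.1902/122 + 0.9098·0.0902/600) = 0.0374
- s1 = √[0.90·0.10·(1/122 + 1/600)] = 0.0298
- power = Φ[(0.10 - 1.645·0.0374)/0.0298] = Φ(1.29) = 90.2%

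The same formula gives 94.6% at 92.5% success and 98.3% at 95%. At 90% success, 122 is the smallest evaluable number that reaches 90% power, and 122/0.94 ≈ 130. The stated power and sample size therefore rest on Rule A.

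**Step 2: probability of declaring non-inferiority under each rule.** Exact enumeration of both binomials, 122 against 600:

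| Comparator success | True Pt - Pc | Rule A | Rule B | Rule C |
|---|---|---|---|---|
| 90% | +5 points | >99.9% | 79.6% | 0% |
| 90% | 0 | 90.1% | 99.1% | 0% |
| 90% | -10 | 4.7% | 100% | 5.3% |
| 90% | -20 | <0.01% | 100% | 79% |
| 90% | -30 | 0% | 100% | >99.8% |
| 92.5% | 0 | 94.3% | 99.9% | 0% |
| 92.5% | -10 | 4.6% | 100% | 5.4% |
| 92.5% | -20 | <0.01% | 100% | 83% |
| 95% | 0 | 97.7% | 100% | 0% |
| 95% | -10 | 4.4% | 100% | 5.5% |
| 95% | -20 | <0.01% | 100% | 86% |
| 95% | -30 | 0% | 100% | >99.9% |

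Rule B runs the wrong way: at 90% comparator success it is less likely to pass when sedation is 5 points better (79.6%) than when it is 10 points worse (100%). Rule C passes with high probability only when sedation is well beyond the margin on the bad side.

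**Step 3: one concrete result.** Suppose 85/122 (69.7%) succeed under sedation and 558/600 (93.0%) in the comparator. The difference is -23.3 points, with one-sided 95% bounds of -30.7 (lower) and -16.7 (upper).

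- Rule A: -30.7 is below -10, so the objective is not met.
- Rule B: -16.7 is below +10, so the objective is met.
- Rule C: -16.7 is below -10, so the objective is met.

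The written sentence declares non-inferiority under either sign of the margin.

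**The case against.** Four points can be made on the other side.

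- **The test is defined correctly apart from this sentence.** The hypotheses, the named test, the alpha and the sample size agree with one another, and a statistician would probably follow them. This is true, and it shows that the fault is one sentence and not the design. The near-100% error applies only to someone who follows that sentence, but it is the sentence that states when the objective is met.
- **A third reading works.** If the difference meant control minus treatment, its upper bound would be minus the lower bound of Pt - Pc, and an upper bound below 0.10 would be the correct rule. The algebra is right. However, the paragraph writes only Pt - Pc and never defines the reverse difference, so the reader would have to supply it.
- **There are later checkpoints.** Appendix E promises a SAP amendment before sub-study enrollment. Section 8.2.3 also bars enrollment until RCT recruitment is complete, the DSMB and FDA have confirmed initial safety, and FDA has approved an IDE Supplement. These lower the practical risk. They do not cure a success criterion already stated wrongly: a correct SAP would contradict the protocol, and one that copied the protocol would repeat the error.
- **It is only a sub-study.** Section 8.5 ties study success to the two RCT primary endpoints, so the RCT conclusions are unaffected. The error is confined to Objective 3.

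**Conclusion.** The concern holds. The decision sentence contradicts the hypotheses directly above it, and nothing elsewhere in the protocol corrects it. With the margin as stated (0.10), the rule passes about 100% of the time at true deficits of 10 to 30 points, against a nominal 5%. With -0.10 it passes 0% of the time at equality and 79-86% at a 20-point deficit. The lower-bound rule gives 4.4-4.7% error at the margin and 90.1-97.7% exact power at equal rates.

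These figures assume 122 and 600 evaluable subjects and comparator success of 90-95%, as the protocol anticipates. The conclusion does not depend on the exact rate: the direction of the rule is wrong throughout that range. It should be corrected before sub-study enrollment begins.

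**What to change.** In Appendix E, J. Sample Size Determination, replace the decision sentence with: the sub-study objective is met if the one-sided 95% lower confidence bound for Pt - Pc, by the Farrington-Manning method, is greater than -0.10. Carry the same wording into the planned SAP amendment.

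Optionally, where the paragraph ends by naming the primary effectiveness endpoint, name Procedure Success at 45 days instead, so that it is not confused with the RCT's 18-month endpoint. This is for clarity only.

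The cost is one sentence in the protocol and its match in the SAP amendment. The margin, alpha, power and the 130 subjects stay as they are, because they were already derived from the lower-bound test.
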